### **5.3. Analysis Populations**

#### **5.3.1. All-Screened Population**

The all-screened population includes all participants who signed the informed consent form. The all-screened population will be used for the summary of analysis populations.

#### **5.3.2. Full Analysis Set**

The FAS includes all participants enrolled in the study who received at least 1 dose of INCB050465.

The FAS will be used for the summary of demographics, baseline characteristics, participant disposition, and all efficacy data.

#### **5.3.3. Safety Population**

The safety population includes all enrolled participants who received at least 1 dose of INCB050465.

All safety analyses will be conducted using the safety population.

[REDACTED]

## **6. BASELINE, EXPOSURE, AND DISPOSITION VARIABLES AND ANALYSES**

[Appendix A](#) provides a list of planned tables, figures, and listings. Sample data displays are included in a separate document.

### **6.1. Baseline and Demographics, Physical Characteristics, and Disease History**

#### **6.1.1. Demographics and Baseline Characteristics**

The following demographics will be summarized and listed for the FAS: age, sex, race, ethnicity, geographic region, weight, height, and BMI. ECOG performance status at baseline will be summarized and listed for the FAS.

#### **6.1.2. Disease History**

Time since initial diagnosis, disease subtype, relationship of MZL to an infection, relationship of MZL to an H. pylori-induced infection, initial cytogenetics, current cytogenetics, initial Ann Arbor stage, current Ann Arbor stage, initial presence of B-symptoms, current presence of B-symptoms, bone marrow involvement (Yes vs No), and relapsed/refractory status to the most recent prior therapy will be summarized and listed for all participants in the FAS. Date of tumor marker tests and test results will be listed.

Time since diagnosis will be calculated as:

$$\text{Time since diagnosis (years)} = (\text{Day 1 date} - \text{date of diagnosis} + 1) / 365.25.$$

#### **6.1.3. Prior Therapy**

Number of prior systemic cancer therapy regimens will be summarized for all participants in the FAS. The component drugs of prior systemic therapy regimens will be coded using the WHO Drug Dictionary. Number and percentage of participants with each drug will be summarized by WHO drug class and WHO drug PT. Regimen name, component drugs, start and stop date, route of the medication, best response, reason for discontinuation, and date of relapse/progression will be listed.

Number of participants who received prior radiation will be summarized for the FAS. Anatomical location of the administration, start and stop date, and total dose will be listed.

Number of participants who had prior surgery or surgical procedure for the cancer treatment will be summarized for the FAS. Date and description of the surgery/procedure will be listed.

Number of participants who had hematopoietic stem cell transplant will be summarized for the FAS. Date of transplant, type of transplant, source of cells, line of therapy, best response, date of relapse/progression, regimen name, and drug used with the transplant will be listed.

#### **6.1.4. Medical History**

Medical history will be coded to SOC and PT using MedDRA coding dictionary. For participants in the FAS, medical history will be summarized by SOC and PT and listed.

## 6.2. Disposition of Participants

The number and percentage of participants who were treated, who were ongoing with study treatment, who discontinued study treatment with a primary reason for discontinuation, who were still in the study, and who withdrew from the study with a primary reason for withdrawal will be summarized and listed for the FAS.

The number of participants enrolled by country and site will also be provided for the FAS.

## 6.3. Protocol Deviations

Protocol deviations recorded on the eCRF will be summarized and listed for the FAS.

## 6.4. Exposure

For participants in the safety population, exposure to INCB050465 will be summarized descriptively as the following:

- **Duration of treatment (days):** Date of last dose – date of first dose + 1.
- **Duration of treatment during the initial QD dosing period (days):** Date of last dose during the initial QD dosing period – date of first dose + 1.
- **Duration of treatment during the maintenance dosing period (days):** Date of last dose – date of first dose during the maintenance dosing period + 1. Crossover participants who switched to the selected treatment regimen after the start of the maintenance dosing period will be summarized in a separate group (ie, Crossover).
- **Average reported daily dose during the initial QD dosing period (mg/day):** total reported dose taken during the initial QD dosing period (mg) / duration of treatment during the initial QD dosing period (days).
- **Average reported daily dose during the maintenance dosing period (mg/day):** total reported dose taken during the maintenance dosing period (mg) / duration of treatment during the maintenance dosing period (days). Crossover participants who switched to the selected treatment regimen after the start of the maintenance dosing period will be summarized in a separate group (ie, Crossover).
- **Dose modifications:** Number of participants who had dose reduction and interruption will be summarized. The number of dose reductions and the number of interruptions for each participant will be summarized.

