• Any recurrent Grade 3 toxicity after 2 dose reductions.	Discontinue INCB050465 administration and follow-up per Protocol. Exceptions require approval of sponsor.
• Any other Grade 4 toxicity.	Discontinue INCB050465 administration and follow-up per Protocol. Exceptions require approval of sponsor.

ALT = alanine aminotransferase; AST = aspartate aminotransferase; CMV = cytomegalovirus; IV = intravenous; ULN = upper limit of normal.

Table 4: Dose Levels and Reductions for INCB050465

Timepoint	Treatment A	Treatment B
Starting dose	20 mg QD for 8 weeks (Day 1 through Day 56)	20 mg QD for 8 weeks (Day 1 through Day 56)
First dose reduction	10 mg QD	10 mg QD
Second dose reduction	5 mg QD	5 mg QD
Week 9 (Day 57) onward	20 mg once weekly ^a	2.5 mg QD ^b
First dose reduction	10 mg once weekly	1 mg QD ^c
Second dose reduction	5 mg once weekly	NA

^a All subjects will receive 20 mg once weekly at Week 9 (Day 57) regardless of prior dose level, unless a dose modification of a switch to a QW schedule before Week 9 is required for diarrhea/colitis management (see Table 5).

^b All subjects will receive 2.5 mg QD at Week 9 (Day 57) regardless of prior dose level, unless a dose modification of a switch to a QW schedule is required for diarrhea/colitis management (see Table 5).

^c Further dose modification due to diarrhea or colitis for subjects on 1 mg QD is permitted (see Table 5).

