
 • Diarrhea (≥ Grade 3). • Noninfectious colitis (any grade; confirmed or suspected). 	
Step 1: Interrupt INCB050465. Perform work-up for infection (including CMV, C. difficile, etc) immediately. Initiate or continue supportive care (see Section 5.4.2). Consider colonoscopy with biopsy for diarrhea ≥ Grade 3 and/or if symptoms^a suggestive of colitis. Monitor every 48 hours until resolution.
 
Step 2: If infection* is ruled out, start oral steroids, or consider IV steroids if participant is being given IV fluids. If no improvement with oral steroids within 48 hours, switch to IV steroids.
 
*For infectious diarrhea/colitis, follow institutional standard of care guidelines and restart parasclisib according to clinical judgement after resolved to ≤ Grade 1. Consult with medical monitor if needed.
 
Step 3: When diarrhea/colitis resolves to ≤ Grade 1, continue supportive care and taper steroids according to institutional standard of care. When taper is complete (eg, no steroid or ≤ 10 mg/day prednisone or equivalent) and diarrhea/colitis is ≤ Grade 1, restart INCB050465 as described herein and with approval of the medical monitor. Continue to monitor.
 
  
 INCB050465 Current Dose	Dose Modification	
   
 Any dose with QD dosing	20 mg QW regardless of Treatment A or B assignment	
 
 20 or 10 mg QW	Restart next lower dose	
 
 5 mg QW	Permanently discontinue	
  
 
Step 4: If ≥ Grade 3 diarrhea/colitis (any grade) reoccurs, permanently discontinue INCB050465.
	INCB050465 Current Dose	Dose Modification	Any dose with QD dosing	20 mg QW regardless of Treatment A or B assignment	20 or 10 mg QW	Restart next lower dose	5 mg QW	Permanently discontinue
INCB050465 Current Dose	Dose Modification								
Any dose with QD dosing	20 mg QW regardless of Treatment A or B assignment								
20 or 10 mg QW	Restart next lower dose								
5 mg QW	Permanently discontinue								

^a Diarrhea accompanied by abdominal pain and/or mucus or blood in stool.

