### **5.2. Treatment Groups**

This is a Phase 2, open-label study. All analyses will be conducted independently for Cohort 1 and Cohort 2, and there will not be multiplicity adjustment between the cohorts. Within each cohort, there will not be any statistical comparison between the treatment groups.

For the purpose of analysis, the 20 mg QW dosing period in Treatment A and the 2.5 mg QD dosing period in Treatment B are considered maintenance dosing periods. Within each cohort, data will be presented in summary tables by actual received treatment regimen and combined, with an exception for participants who cross over to the selected treatment regimen after the start of the maintenance dosing period.

For participants who cross over from the initially assigned treatment regimen to the selected treatment regimen, if the crossover happens before/on the start of the maintenance dosing period, then the participant will be summarized, according to the actual received treatment, in the selected treatment regimen; otherwise, the participant will be summarized in:

- A separate treatment regimen (ie, Crossover) for the safety summaries during the maintenance dosing period (eg. summaries of TEAEs and exposure).
- The initially assigned treatment regimen for all other summaries.

Per Protocol Amendment (Version) 3, Cohort 1 was closed to further enrollment. If the number of participants who have enrolled in Cohort 1 is relatively few, summary tables will be replaced with listings.

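### SAP 6.4 leaves a hold that is still running at the end of Day 56 and ends in a maintenance restart outside both period durations, so the period average daily doses omit it

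*SAP*

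**What the plan says.** SAP 6.4 (Exposure) defines the initial-period duration as "Date of last dose during the initial QD dosing period – date of first dose + 1" and the maintenance duration as "Date of last dose – date of first dose during the maintenance dosing period + 1". The initial average reported daily dose is "total reported dose taken during the initial QD dosing period (mg) / duration of treatment during the initial QD dosing period (days"). The maintenance average is built in the same way. Overall duration runs from first to last dose, and no average dose is planned over it.

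The SAP gives no calendar dates for the initial period. SAP 5.2 says only that "the 20 mg QW dosing period in Treatment A and the 2.5 mg QD dosing period in Treatment B are considered maintenance dosing periods". The dates come from Protocol Table 4 (section 5.4.1.1), which plans the 20 mg daily phase for Days 1 to 56. For Treatment B its footnote says "All subjects will receive 2.5 mg QD at Week 9 (Day 57) regardless of prior dose level", with an exception for a switch to weekly dosing for diarrhea/colitis. The Treatment A footnote is parallel.

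Protocol 5.4.1 allows interruptions of up to 14 days, and longer ones after discussion with the sponsor. For some diarrhea and colitis events, Table 5 makes restart wait until a steroid taper is finished.

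**The concern.** Both durations are anchored on doses taken, so neither contains the days between the last initial dose and the first maintenance dose. In an uninterrupted course there are no such days. When a hold spans the change of regimen, all of it lies there.

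The rule is therefore inconsistent. It is not a convention of counting only time on drug, because holds inside a period stay in the denominator. Whether a hold lowers the average depends on whether one more dose of the same phase follows it. The error has one direction: for affected participants the period average is too high. These averages have their own outputs (Tables 3.1.2 and 3.1.3), and a reader will use them to judge how much of the 20 mg phase was delivered.

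**Working it through.** SAP 6.4 states no numeric result, so there is no figure to reproduce. The formulas were applied to day-by-day dosing records.

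**Inputs from the documents:** the SAP 6.4 formulas; 20 mg daily on Days 1–56 and 2.5 mg daily from Day 57 (Protocol Table 4, Treatment B).

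**Assumptions:** last dose on Day 168; full dose on every dosed day; hold dates chosen for illustration.

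**Formulas**
- SAP initial average = 20 × (doses taken on Days 1–56) / (day of last initial dose).
- SAP maintenance average = 2.5 × (maintenance doses) / (168 − day of first maintenance dose + 1).
- Comparison: the same totals divided by 56 days (Days 1–56) and 112 days (Days 57–168).
- Days in neither period = 168 − initial duration − maintenance duration.

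| Hold (days) | SAP initial average | Over Days 1–56 | SAP maintenance average | Over Days 57–168 | Days in neither |
|---|---|---|---|---|---|
| none | 1120/56 = 20.00 | 20.00 | 2.50 | 2.50 | 0 |
| 22–35 | 840/56 = 15.00 | 15.00 | 2.50 | 2.50 | 0 |
| 42–55 | 840/56 = 15.00 | 15.00 | 2.50 | 2.50 | 0 |
| 43–55 | 860/56 = 15.36 | 15.36 | 2.50 | 2.50 | 0 |
| 43–56 | 840/42 = 20.00 | 15.00 | 2.50 | 2.50 | 14 |
| 50–63 | 980/49 = 20.00 | 17.50 | 262.5/105 = 2.50 | 262.5/112 = 2.34 | 14 |
| 57–70 | 20.00 | 20.00 | 245/98 = 2.50 | 245/112 = 2.19 | 14 |
| 64–77 | 20.00 | 20.00 | 245/112 = 2.19 | 2.19 | 0 |
| 29–56 | 560/28 = 20.00 | 10.00 | 2.50 | 2.50 | 28 |

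**Reading the table**
- Holds on Days 42–55 and Days 43–56 have the same length and the same number of initial doses, yet give 15 and 20 mg/day. The second is 20/15 = 1.33 times the calendar figure.
- Extending a hold from Days 43–55 to Days 43–56 means one dose fewer, but raises the reported average from 15.36 to 20.00.
- For the Day 43–56 hold, the durations sum to 42 + 112 = 154 of 168 days.
- A hold that begins on Day 57, before any maintenance dose, drops out in the same way on the maintenance side.
- Treatment A gives the same initial-period figures and the same 14-day gap for the Day 43–56 hold.

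**Trial-level size (assumed prevalence).** If a share p of participants had the Day 43–56 pattern, the mean initial dose would be overstated by p × (20 − 15) mg/day: 0.1 at 2%, 0.25 at 5%, 0.5 at 10%, 1.0 at 20%.

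**Compliance.** SAP 6.5 divides by the prescribed dose after allowing for dose modifications. On that wording, days on a prescribed hold are not recovered there.

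**The case against.** The strongest answer is that the holds remain visible elsewhere. SAP 6.4 summarizes participants with interruptions and interruptions per participant. SAP 9.2.3 reports participants who interrupted because of TEAEs for the initial, maintenance and overall periods, and tabulates the events that led to interruption. Study drug administration is listed. Table 3.1.2 puts duration beside average dose, so the Day 43–56 case reads 42 days at 20 mg/day, and the product is still 840 mg. A reader might infer that the plan conceals late toxicity holds; it does not. What no planned summary gives is the number of days on hold.

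A reader might also infer that the SAP claims full dose intensity, or that tolerability of the 20 mg phase will be misreported. The SAP calls the quantity an average reported daily dose and makes no claim of relative dose intensity. Tolerability rests mainly on the adverse event summaries in SAP 9.2.

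The frequency is also open to challenge. Protocol 5.4.4 says most immune-related events occur after the first 9 weeks, so boundary-spanning holds may be a minority. Under Protocol 5.5.1, an AE-related delay beyond 14 days requires withdrawal from treatment unless the sponsor approves longer, so the 28-day row is an exception.

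All of this stands and limits the point. It does not remove the inconsistency: two equal holds one day apart give 15 and 20 mg/day under one stated rule.

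**Conclusion.** The point holds as a minor flaw in a descriptive exposure summary. A hold still running at the end of Day 56 and followed by a maintenance restart is in neither period duration, and the period average daily dose is overstated for that participant. For a 14-day hold on Days 43–56, the reported figure is 20 instead of 15 mg/day. It equals exactly 20 only if every earlier dose was full; after a reduction or missed dose it is lower but still too high.

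The trial-level effect is unknown because the documents give neither the frequency nor the timing of holds; the prevalence range above is illustrative. Participants who never restart are not part of this inconsistency. No efficacy result changes.

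One related point is undefined. Under Protocol Table 5, a participant on daily dosing who is held for Grade 3 or higher diarrhea or for noninfectious colitis restarts on weekly dosing whatever the assignment. SAP 5.2 defines Treatment B maintenance only as the 2.5 mg daily period. The documents do not say which exposure period such a Treatment B participant is then in, and the passages must be reconciled for this analysis.

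**What to change.** In SAP 6.4, for participants who enter maintenance:
- End the initial period on the later of (a) the last dose taken in the initial once-daily period and (b) the earlier of Day 56 and the day before the first maintenance dose.
- Start the maintenance period on the next day.
- Use these durations as denominators and assign doses to the same periods. The two durations then add up to the overall duration.

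Part (a) is needed. Visits have a ±3-day window in Protocol Table 6. If 20 mg daily dosing ran to Day 59 (assumed), a flat Day 56 cap would give 1180/56 = 21.1 mg/day, above the planned dose; the rule above gives 1180/59 = 20. Part (b) also covers a move to weekly dosing before Week 9 in Treatment A.

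For participants who never enter maintenance, keep the last dose as the end and footnote that a terminal hold is not counted: a hold from Day 43 followed by discontinuation still reads 20 mg/day.

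State which period applies to Treatment B participants moved to weekly dosing for diarrhea/colitis. A summary of days on hold would be a useful optional addition.

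The cost is SAP wording and one derivation. The downside is that reported average daily doses become lower for affected participants.

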An additional 30 participants will be enrolled into one of the two treatment regimens (A or B) being evaluated in this study to better understand the safety and efficacy of INCB050465. The treatment regimen will be selected after enrollment is completed for Cohort 2 (ie, 60 participants enrolled) and will be selected after evaluation of emerging safety and efficacy data from this and other monotherapy studies of INCB050465 in non-Hodgkin's lymphoma. Once a treatment regimen is selected, the non-selected treatment regimen will be closed to further enrollment. Participants receiving the non-selected treatment regimen may switch to the selected treatment regimen or remain on their current treatment regimen, provided the participant has not met study-treatment withdrawal criteria and there are no safety concerns for their current treatment regimen. There will be no re-baselining for participants who switch treatment regimens and all participants will continue to follow the same assessment schedule.

Participants will receive treatment until disease progression, death, unacceptable toxicity, or consent withdrawal. Participants will be evaluated for ORR by an IRC and followed for DOR, PFS, OS, and safety.

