#### **4.1.4. Handling of Missing and Incomplete Data**

In general, values for missing data will not be imputed unless methods for handling missing data are specified in this section or relevant sections. The original reported dates collected on the eCRF should be used in all relevant listings. The following rules will be used for handling missing or partial dates for analyses requiring dates.

When calculating time since initial diagnosis of cancer, partial diagnosis date will be handled in the calculation as follows:

- If only the day is missing, then the first day of the month will be used.
- If both the month and day are missing, then 01 JAN will be used.
- Otherwise, the time since diagnosis will not be calculated.

When the date of the last dose is used in deriving variables such as duration of treatment or TEAE flag, missing or partial date of last dose will be handled in the calculation as follows:

- If only the day is missing, then the earlier date of the last day of the month or the date that the participant discontinued treatment will be used.
- If both the month and day are missing, then the earlier date of 31 DEC of the year or the date that the participant discontinued treatment will be used.
- Otherwise, the date that the participant discontinued treatment will be used as the date of the last dose.

When calculating DOR, PFS, and OS, a partial date of death will be handled in the calculation as follows:

- If mmyyyy for the last known alive date = mmyyyy for the death date, then the day after the last known alive date will be used.
- If mmyyyy for the last known alive date < mmyyyy for the death date, then the first day of the death month will be used.
- Otherwise, the partial death date will not be handled.

When calculating time to onset or duration of a TEAE, a partial or missing AE onset/end date will be handled in the calculation as follows:

- If only the day is missing, then the first day of the month or Day 1, whichever is later, will be used as the onset date; the earlier date of the last day of the month or the date that the participant discontinued study or died will be used as the end date.
- If both the month and day are missing, then 01 JAN or Day 1, whichever is later, will be used as the onset date; the earlier date of 31 DEC or the date that the participant discontinued study or died will be used as the end date.
- Otherwise, Day 1 will be used as the onset date, and the missing end date will not be handled.

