### Amendment 1 (27 AUG 2020)

- Section 4.1.4 was updated to include details of rules for handling partial/missing onset or end date of TEAEs in the calculation of time to onset or duration of a TEAE. Rules for partial/missing date of last dose were updated to include details of handling situations where both month and day are missing.
- Section 5.2 was modified to provide details regarding how crossover participants will be summarized.
- Section 5.3 was updated to remove the efficacy evaluable analysis set and use the FAS for all analyses on efficacy data. This change is to comply with comments from FDA that any participants who received at least 1 dose should be included in the efficacy analyses for a single-arm trial. The all-screened population was added for the summary of analysis populations.
- Section 6.1.2 was modified to remove summaries of tumor markers but only keep listings. Relapsed/refractory status to the most recent prior therapy was added to the summary table of disease history because the response to last regimen before entering the study may be a prognostic factor for clinical outcomes.
- Section 6.2 was modified to add summaries of participants who are ongoing with treatment or still in the study.
- Section 6.4 was modified to change the calculations of duration of treatment and average dose during the maintenance dosing period because Group B with 2.5 mg QD was selected as the maintenance dose.
- Section 7.3 and Section 7.4 were modified to add efficacy analyses for participants in the FAS who have at least 2 prior therapies to support an indolent NHL indication in the same line of therapy as with follicular lymphoma in Study INCB 50465-203.
- Section 7.3.1 was modified to replace the efficacy evaluable analysis set with the FAS. This change is to align with Protocol Amendment 4 dated 23 DEC 2019 and include all treated participants in the efficacy analyses to comply with comments from FDA.
- Section 7.3.2 was modified to add "unknown" as a category for bone marrow involvement at baseline. Relapsed/refractory status to the most recent prior therapy was added to the subgroup analysis because the response to last regimen before entering the study may be a prognostic factor for clinical outcomes.
- Section 7.4.3 was modified to update references of censoring for PFS.

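### SAP 6.4 counts the last weekly maintenance dose as one day instead of seven, so average daily dose on 20 mg weekly is at most 2% too high at the expected treatment length but far too high after one to four doses (descriptive only)

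*SAP*

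**What the plan says.** SAP 6.4 measures maintenance duration as the last-dose date minus the "date of first dose during the maintenance dosing period + 1". It then defines average daily dose in maintenance as "total reported dose taken during the maintenance dosing period (mg) / duration of treatment during the maintenance dosing period (days"). Nothing in 6.4 adds the dosing interval that follows a final weekly dose.

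SAP 5.2 states that "the 20 mg QW dosing period in Treatment A and the 2.5 mg QD dosing period in Treatment B are considered maintenance dosing periods" and presents data by regimen received and combined, so the one formula applies to both schedules.

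Weekly dosing does not disappear once a regimen is chosen. SAP 3 says: "Participants receiving the non-selected treatment regimen may switch to the selected treatment regimen or remain on their current treatment regimen". The change log in SAP 11.2 (Amendment 1) records that the maintenance duration and average-dose calculations in 6.4 were changed "because Group B with 2.5 mg QD was selected as the maintenance dose".

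SAP 4.1.4 governs missing or partial last-dose dates. It can substitute a month end, a year end or the treatment discontinuation date; its final rule reads: "Otherwise, the date that the participant discontinued treatment will be used as the date of the last dose".

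The result appears in Table 3.1.3 (SAP Appendix A). SAP 5.1 includes the mean, standard deviation, median, minimum and maximum in descriptive summaries.

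**The concern.** A daily average needs a numerator and a denominator that cover the same time. With daily dosing they do: each dose brings its own day. With weekly dosing every dose but the last brings seven days, and the last brings one. The final dose therefore counts in full in the numerator but for one seventh of its interval in the denominator.

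The nominal gap between the maintenance regimens is small: 2.86 − 2.50 = 0.36 mg/day. The excess in an individual average can be of similar size or larger. It is 3.08 − 2.86 = 0.22 mg/day after 12 weekly doses and 3.64 − 2.86 = 0.78 mg/day after four. A participant who takes one weekly dose and stops is reported at 20 mg/day, the rate of the initial daily phase that maintenance steps down from. At stake is how someone reading the exposure table understands Treatment A, particularly its maximum and standard deviation.

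**Working it through.** The SAP states no numerical average dose, so there is no figure of its own to reproduce. The check applies the 6.4 formula to on-schedule dosing with recorded dates.

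**Inputs.**
- Maintenance doses: 20 mg weekly or 2.5 mg daily (SAP 3).
- Denominator: D = last-dose date − first maintenance-dose date + 1 (SAP 6.4).
- Expected treatment period: about 52 weeks (Protocol synopsis). Less the 8 daily-dosing weeks this leaves 44 weekly doses.

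**Daily dosing.** n doses span D = n days, so the average is 2.5n/n = 2.5 mg/day for every n. This is exact.

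**Weekly dosing.** n doses span D = 7(n − 1) + 1 = 7n − 6 days, so the average is 20n/(7n − 6). With a full interval credited to the last dose the denominator is D + 6 = 7n, and the average is 20/7 = 2.857 mg/day. The relative excess is (D + 6)/D − 1 = 6/D.

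| Weekly doses | D (days) | 6.4 average (mg/day) | Excess over 2.857 |
|---|---|---|---|
| 44 | 302 | 880/302 = 2.914 | +2.0% |
| 19 | 127 | 380/127 = 2.992 | +4.7% |
| 12 | 78 | 240/78 = 3.077 | +7.7% |
| 4 | 22 | 80/22 = 3.636 | +27.3% |
| 2 | 8 | 40/8 = 5.0 | +75% |
| 1 | 1 | 20/1 = 20.0 | +600% |

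The excess falls below 5% once D exceeds 120 days. At 18 doses D is exactly 120, so 19 is the first count below 5%. The dose level cancels: four doses of 10 mg weekly give 40/22 = 1.818 against 10/7 = 1.429, again +27.3%.

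**These are maxima.** If observation ends with only k days of the last interval elapsed, the ratio is (D − 1 + k)/D. For four doses, k = 5 gives 26/22 (+18%) and k = 3 gives 24/22 (+9%).

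**An imputed date can reverse the direction.** Suppose, as an assumption, that four weekly doses were taken and the last-dose date is imputed 20 days late. Then D = 42 and the average is 80/42 = 1.90 mg/day, 33% below nominal.

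**Effect on a group summary.** The documents give neither the number of participants on Treatment A nor the number who stop early. Assume 30 participants, 29 of them with 44 doses (2.914 mg/day):

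- No early stopper: mean 2.914 (+2.0%).
- The 30th takes four doses: (3.636 + 29 × 2.914)/30 = 2.94 (+2.8%).
- The 30th takes two doses: (5 + 29 × 2.914)/30 = 2.98 (+4.4%).
- The 30th takes one dose: (20 + 29 × 2.914)/30 = 3.48 (+22%).

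The median is 2.91 in all four cases. In the single-dose case the maximum is 20 mg/day and the standard deviation is (20 − 2.914)/√30 = 3.1 mg/day. With full intervals credited, every participant would show 2.857 and the standard deviation would be zero.

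**The case against.** The strongest reply is that this is a convention, not a mistake. First-to-last-dose duration is an accepted definition, the formula returns what it defines, and 2.86 mg/day is the reference only if seven days are credited to the last dose. The first part stands: the duration summary is not disputed. But the quantity is labelled a daily dose, and one tablet intended for a week is reported as 20 mg/day. The convention does not carry over to that denominator.

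The SAP 11.2 log also suggests that the calculation was revised with the selected daily regimen in mind, and for that regimen it is exact. That is fair, and it limits the issue mainly to participants who stayed on Treatment A or stopped on it. The log does not give the former formula or say that the weekly case was considered.

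The effect is about 2% at the expected treatment length, medians are reported, and Listing 2.5.2 covers individual drug administration. All of this stands. The table shells are in a separate document, so whether a footnote already exists cannot be checked.

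A reader might go further in three ways that the documents do not support:

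- That the average is always overstated. This fails where SAP 4.1.4 imputes a late last-dose date.
- That Treatment A's reported exposure is inflated several-fold. That describes one participant who stops after a single weekly dose, and the documents give no count of such participants.
- That the percentages above apply to participants moved to "20 mg QW regardless of Treatment A or B assignment" under Protocol Table 5. Earlier daily dosing in the same period dilutes the excess: with 140 daily-dosing days and four weekly doses, D = 162 and the excess is 6/162 = 3.7%. The treatment interruption before the restart lowers it further.

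**Conclusion.** The point holds as a minor one. Followed as written, SAP 6.4 gives a correct daily average for 2.5 mg daily and a biased one for on-schedule 20 mg weekly. The excess of 6/D is negligible for long treatment and large only for participants who stop within a few weeks of starting maintenance. The stated sizes assume a recorded last-dose date, weekly dosing on schedule throughout maintenance, and a full seven-day interval after the last dose.

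The consequence is confined to descriptive exposure in Table 3.1.3: chiefly the Treatment A maximum and standard deviation, and possibly the mean. A reader might infer that efficacy or safety conclusions are at risk; they are not. ORR, DOR, PFS and OS do not use this average. TEAE flags use the last-dose date itself, and compliance in SAP 6.5 divides dose taken by dose prescribed. SAP 5.2 plans no statistical comparison between regimens.

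**What to change.** Add a rule to SAP 6.4 for the denominator of average daily maintenance dose only. When the last maintenance dose was weekly and its date was recorded rather than imputed, use D + 6 days, truncated at the earliest of death, data cutoff, start of new anticancer therapy or start of the next dosing schedule. Where the last-dose date was imputed under SAP 4.1.4, add nothing, because that date may already lie beyond the last dose. Leave the duration summaries and the last-dose date used for adverse event windows unchanged. Footnote the convention in Table 3.1.3.

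Without truncation the rule returns 20n/(7n) = 2.86 mg/day for every n and leaves daily dosing at 2.5 mg/day. Where truncation applies, a very early stopper can still show a high value, but it then reflects the days actually observed.

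The cost is a short addition to the SAP, one derivation with a few truncation rules, and a footnote. The drawback is that the denominator will differ from the duration shown in the same table and can include up to six days after the last tablet; the footnote should say so.

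No dose, schedule or efficacy analysis changes.
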